1.0 Background

Subacromial impingement syndrome is a commonly encountered shoulder condition that consists of a constellation of symptoms, including pain with overhead activities. As the condition progresses, the pain may manifest at night, associated or not with progressive loss of motion and strength of the shoulder [1-3]. Impingement-related pain is thought to result from subacromial bursitis and tendonitis of the supraspinatus due to repetitive overhead activities impinging the coracoacromial arch [3, 4]. Many non-operative treatments have been advocated for subacromial impingement syndrome, beginning with rest, ice, oral non-steroidal anti-inflammatory drugs (NSAIDs), and physical therapy [5, 6]. If patients fail to improve with conservative therapy, subacromial injections could be utilized to treat this condition [2, 7-11]. Although the exact mechanism(s) of corticosteroids and NSAIDs is/are not completely understood, it is hypothesized that symptom relief post subacromial injections is related to their local anti-inflammatory properties [2, 12].

While studies comparing subacromial injection of NSAIDs to steroids exist, they are low-powered or lack long follow-up. Karthikeyan et al. conducted a randomized controlled trial in 2010 that compared subacromial injections of 40 mg methylprednisolone versus 20 mg of tenoxicam for subacromial impingement [13]. Their outcomes were the Disability of Arm, Shoulder, and Hand (DASH) score and the Oxford Shoulder Score (OSS). They concluded that corticosteroids are significantly better than tenoxicam for improving shoulder function in tendonitis of the rotator cuff, but their follow-up was only six weeks. Min et al., on the other hand, conducted a similar randomized controlled trial in 2013 using 40 mg triamcinolone versus 60 mg ketorolac [3]. Their outcome measures were the visual analog (VAS) and the University of California Los Angeles (UCLA) shoulder rating scales. They showed greater improvements in the UCLA rating scale in the ketorolac arm, but their follow-up was only four weeks. Taheri et al. conducted a randomized controlled trial in 2017 to compare subacromial injections of 60 mg ketorolac and 40 mg methylprednisolone [14]. Their outcome measures were the VAS and Constant's score. While the results did not show any significant difference between the two therapeutic arms at three months' follow-up, the study included only 40 patients and an a priori power analysis was not performed. The lack of long-term follow-up and the inadequate power in the aforementioned studies point to the need for further investigation.

If it can be shown that subacromial NSAIDs are superior or equivalent to steroids, the benefits to society could be multiple. Bellamy et al. studied the economic impact of using ketorolac instead of steroid for the treatment of knee osteoarthritis over a three-year period [15]. They found a total potential cost savings of approximately \$12,000 if ketorolac was used in place of steroids at their institution. Furthermore, the local tissue reaction of steroids may be mitigated with the use of ketorolac. Shapiro et al. compared injections of methylprednisolone versus ketorolac in a rabbit model [16]. They found that the rabbits injected with steroids demonstrated greater peri-tendinous adhesions and cartilage necrosis compared to the rabbits injected with ketorolac and normal saline.

2.0 Rationale and Specific Aims

Because of the current conflicting evidence, the lack of long-term follow-up, and the multiple potential benefits to the society, we aim to compare subacromial ketorolac versus steroid for the treatment of shoulder impingement. We hypothesize that patients with external shoulder impingement who are treated with a subacromial injection of 80 mg methylprednisolone in 1% lidocaine versus 60 mg ketorolac in 1% lidocaine have similar outcomes based on the American Shoulder and Elbow Surgeon (ASES) self-assessment score (ranging between 0 and 100) at 2, 4, and 12 weeks post-injection. If the follow-up could not be performed exactly at 2, 4, or 12 weeks post-injection, investigators will allow examination and measurements at ± 3 days. The study will be performed in The University of Texas Medical Branch (UTMB, coordinating center). This will help us determine the efficiency of either therapeutic modality in the management of patients with subacromial impingement syndrome.

3.0 Inclusion/Exclusion Criteria

The center enrolling patients (UTMB) will obtain approval through its own institution review board (IRB). The study will be posted on clinicaltrials.gov. The subjects in this study will be recruited from the investigators' private clinics. Prior to enrollment, the investigator will obtain informed written consent from the subjects. All of the investigators are CITI trained. They will review the consent form with patients and allow sufficient time for potential subjects to read the consent form and consider the risks and benefits of participation. Investigators will leave the clinic room to allow patients to consult with friends and family. If patients decide to defer the decision to enroll, they will be allowed to return at a later date. It will be emphasized to patients that they need not participate in the study to receive a subacromial injection. If they choose not to participate, they will be offered a subacromial injection that consists of the medication that is mutually agreed upon between their physician and them. No coercion to participate in the study will take place.

Adults at least 18 years of age seen in clinic with a diagnosis of severe or recalcitrant shoulder impingement syndrome and to whom the investigator has offered a subacromial injection will be invited to participate.

Subjects meeting any of the exclusion criteria at baseline will be excluded from study participation. Exclusion criteria are: allergy/intolerance to steroids or NSAIDs symptoms less than one month, pregnancy or breastfeeding, pre-existing asthma, uncontrolled psychiatric illness, previous shoulder injection within the past three months, evidence of other confounding shoulder pathology on plain radiographs such as calcific tendonitis, MRI evidence or history of a full-thickness rotator cuff tear, active comorbidities of the ipsilateral extremity such as cervical radiculopathy, moderate to severe glenohumeral arthritis, systemic inflammatory conditions, kidney or liver disease, gastrointestinal (GI) ulcers, bleeding disorders, pending litigation or work-related claims related to the shoulder, previous shoulder surgery on the affected shoulder, evidence of local infection, evidence of adhesive capsulitis, and evidence of shoulder instability.

4.0 Treatment Assignment/Randomization

The following measures will be taken to ensure double-blinded randomization. Prior to the initiation of the study, computer-generated tables will be created in Excel to assign each patient a randomization number. This master list will be kept with a statistician and research coordinators, who do not have any patient contact. Based on his/her corresponding generated number (even or odd), the patient will be assigned to his/her therapeutic arm (methylprednisolone and ketorolac, respectively). The statistician will use an equally weighted random number generator to create these assignments. Therefore subjects will have an equal chance of being assigned to either treatment arm. Separate lists for male and female participants will also be generated to ensure equal gender participation. The statistician will then prepare an opaque envelope for each subject number. The unique subject number will be written on the visible outside surface of each envelope. The corresponding treatment arm assignment will be inside the envelope. The statistician will seal each envelope individually and send all of the envelopes to the research coordinator ([name]) prior to patient enrollment. The sealed opaque envelopes will be divided equally among the clinics and kept in locked containers in the research coordinator's office. The study staff will not have access to the envelopes. After ensuring that the patient has completed the ASES questionnaire (to establish a baseline prior to the injection), the study staff will contact [name] or [name] to provide them with the patient's first and last names as well as the MRN. The research coordinator will open one of the sequentially numbered envelopes to assign each patient the corresponding subject number (written on the outside of the envelope), and a member of the clinic staff will prepare the appropriate injection (see below) for the assigned treatment arm. The syringe will be covered with opaque tape prior to being given to the surgeon for administration. The injection will take place in a private clinic room in compliance with the Health Insurance Portability and Accountability Act (HIPAA) guidelines. The blinded surgeon will administer the injection into the subacromial space using standard bony landmarks from the posterolateral approach. The clinic staff will file the drug accountability log after preparing the injection and they will not disclose the treatment arm assignment to the patient nor the provider. This will maintain the blinding for both the patient and research surgeons. Patients' subject number will be recorded on their consent form and in their electronic medical record. Envelopes will be destroyed at the end of the study by the research coordinators. The statistician will unlock the master list only after patient enrollment and follow-up are complete, or if mandated by any regulatory body. Blinding will also be uncovered in case of a patient developing an adverse event while being followed in the trial.

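### Section 4.0 gives the master allocation list to the role that also opens the envelopes, is inconsistent on whether that role can read it, and does not require the next envelope in sequence

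*Combined protocol and SAP*

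**What the plan says.** All of the following comes from Section 4.0 unless another section is named.

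- **Custody of the list.** "This master list will be kept with a statistician and research coordinators, who do not have any patient contact".
- **From list to arm.** "Based on his/her corresponding generated number (even or odd), the patient will be assigned to his/her therapeutic arm": even for methylprednisolone, odd for ketorolac. The generator is equally weighted, and there are separate lists for men and women.
- **Envelopes.** They are opaque and carry the subject number on the outside. "The statistician will seal each envelope individually and send all of the envelopes to the research coordinator". They are divided among the clinics and "kept in locked containers in the research coordinator's office".
- **Assignment.** After the baseline ASES is complete, study staff contact two persons (names removed) "to provide them with the patient's first and last names as well as the MRN". Then: "The research coordinator will open one of the sequentially numbered envelopes to assign each patient the corresponding subject number".
- **Lock.** "The statistician will unlock the master list only after patient enrollment and follow-up are complete, or if mandated by any regulatory body". Blinding is also lifted for a patient who has an adverse event; Section 7.0 has the statistician do this.
- **Afterwards.** The subject number goes on the consent form and into the medical record, and clinic staff file a drug accountability log. "Envelopes will be destroyed at the end of the study by the research coordinators".

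Section 6.0 describes a different procedure: envelopes are held in each investigator's clinic, and study staff alone have access, open them and prepare the injection.

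**The concern.** Allocation concealment requires that whoever assigns a patient can neither foresee nor choose the arm. A sealed opaque envelope gives no protection against someone who can read the list behind it. Section 4.0 places custody of the list and the opening of envelopes in one role, and the opening follows a call that identifies the patient. Lack of patient contact limits the risk but does not remove it, because a name and record number are enough to identify the patient.

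Two safeguards that would matter if the list were readable are also missing. No rule says which envelope must be opened, and the envelopes are destroyed by the role that opened them. In a trial of 40 patients, a few steered assignments could move the treatment comparison. The weakness lies within Section 4.0, so choosing that section over Section 6.0 as the governing text would not cure it.

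**Working it through.** **1. Can the assigner read the list?** Three statements bear on this: the coordinators keep the list, the number's parity gives the arm, and the statistician unlocks the list only at the end or on a regulator's mandate. They allow two readings.

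- *The coordinators' copy is readable.* The role that opens the envelopes could then look up future assignments, and the lock sentence is not true of that copy.
- *The copy is locked.* Concealment is kept, but the plan states no use for the copy, because revealing the arm after an adverse event falls to the statistician (Section 7.0).

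The text does not decide between them. On either reading, nothing that the plan describes is lost if the coordinators hold no copy.

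**2. Can the assigner choose the envelope?** Sequential numbering implies an order of use, but no sentence imposes it. Lists separated by sex and envelopes divided among clinics mean that several sequences may be open at once, so the next envelope is undefined. No step ties a patient to an envelope before it is opened.

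Illustration, assuming a readable list, free choice and 1:1 simple randomization: the chance that at least one of k unopened envelopes holds a wanted arm is 1 − 0.5^k.

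| k | Chance |
|---|---|
| 1 | 50% |
| 2 | 75% |
| 3 | 87.5% |
| 5 | 96.9% |

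If the next envelope must be taken, the opener has no choice of arm.

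**3. What could steering do?** Inputs from Section 9.0: SD 12.3, Δ = 12, one-sided α 0.05 (z printed as 1.64), 40 patients, 20 per arm. The plan's own figure reproduces: 4 × (1.64 + 0.84)² × 12.3² / 12² = 25.85, so 26; 26 / 0.8 = 32.5, so 33. The plan then aims for 40. The concern changes none of these figures.

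Assumptions not in the documents: each exchange swaps one good-prognosis and one poor-prognosis patient who differ by 12 ASES points, all exchanges run in the same direction, and all 20 per arm complete.

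- Shift per exchange: 12/20 + 12/20 = 1.2 points.
- Two exchanges: 2.4 points, and 2.4 / 12 = 20% of Δ.
- Standard error of the difference: 12.3 × √(2/20) = 3.89. The shifts are 1.2 / 3.89 = 0.31 and 2.4 / 3.89 = 0.62 standard errors.
- Treating 12 as the non-inferiority margin (also an assumption), with a true deficit of 12 and exchanges favoring ketorolac, the false non-inferiority rate rises from 5% to 1 − Φ(1.645 − 0.31) ≈ 9% for one exchange and 1 − Φ(1.645 − 0.62) ≈ 15% for two.

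The shifts scale with the assumed gap: a 6-point gap gives 0.6 and 1.2 points.

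**4. What record would remain?** Subject numbers on consent forms and charts, the drug accountability log (Section 4.0), the inventory log at each location (Section 6.0) and the statistician's list. Together these could expose out-of-sequence use. None is said to record when each envelope was opened, or that the patient was tied to it beforehand.

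**The case against.** The strongest reply is that the lock sentence settles the matter: the coordinators hold a locked file, perhaps as a backup, and sealed envelopes hide the arm until opened. Numbering envelopes has little purpose unless they are used in order, and the loose wording may only reflect several parallel lists. Section 5.0 also mentions a Study Drug Management Form that covers randomization and may hold the missing rules; it is not among the documents.

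Much of this stands, and it rules out four stronger readings that a reader might infer.

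- *That all 40 assignments are knowable in advance to the person making them.* The lock sentence prevents that conclusion. The text is inconsistent on access and does not establish it.
- *That steering would leave no record.* The consent forms, charts and drug logs contradict this.
- *That the outside number reveals the arm by its parity.* If sequential subject numbers set the arm by even or odd, the arms would alternate, contrary to the stated random generator.
- *That the persons told the name and record number are certainly the coordinators.* Their names are removed, so this is an inference, although the coordinator opens the envelope in any case.

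Section 9.0 also provides for baseline ASES adjustment if baseline scores differ, which would absorb some steering on baseline severity.

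The reply does not remove the custody rule itself, which is stated and not merely left open. Nor does it supply a rule for which envelope to open, or a reason to destroy the envelopes.

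**Conclusion.** The point holds as a weakness in how concealment is specified. Section 4.0 combines custody of the list with the opening of envelopes, contradicts itself on access to the list, leaves the order of use unstated and discards the envelopes. It does not show that the assigner knows or chooses the arm; that follows only if the coordinators' copy is readable and the choice of envelope is free.

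The size cannot be derived from the documents. The 1.2-point and 2.4-point shifts, and the error rates of about 9% and 15%, illustrate what one or two exchanges would do under the assumed gap, direction and margin. They are not estimates of bias in this trial. The change should be made because it closes a gap in a small trial at very little cost.

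**What to change.** In Section 4.0:

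1. State that the statistician alone holds the master list and that the coordinators hold no copy.
2. Replace the opening rule with one requiring the next unopened envelope in sequence within the list for the patient's sex, and within the clinic's allotment if envelopes are divided by clinic.
3. Have the coordinator write the patient identifier, date and time on the sealed envelope before opening it.
4. Keep opened envelopes with the study records and check them against the master list at unblinding, in place of destroying them at study end.

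Items 1 and 2 work together: the first removes foreknowledge and the second removes choice. Section 6.0 must be reconciled with Section 4.0 on where envelopes are kept, who has access and who opens them.

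The cost is wording, a brief logging step for each patient, one check at unblinding and storage of about 40 envelopes.

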In this formula, Δ represents the absolute difference between the means (μ) of groups 1 and 2 ($\Delta=|\mu_2 - \mu_1|$); σ , the variance of the mean; n, the sample size per arm; α , the probability of type 1 error (0.05); β , the probability of type II error (0.2); and z, the critical z value for a given α or β . To this end, 13 individuals per arm (26 in total) should have been enrolled and completed the trial. Assuming that 20% of patients will be lost to follow-up [3], we will attempt to enroll $26/0.8 = 33$ patients. For this end, we would aim at including a total of 40 patients in the study, which correspond to 20 patients per therapeutic arm. We will also assess whether there are differences in baseline scores between the 2 groups. In the case that the ASES scores differ, we will control for baseline value for each patient by including it as a covariate in a linear regression analysis, with covariates being baseline value and treatment group.

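### Section 4.0 describes simple randomisation with no stated restriction, so neither 20 per arm nor balance within sex is assured; the power cost is small and permuted blocks within each sex list would fix it.

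*Combined protocol and SAP*

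**What the plan says.** Section 4.0 (Treatment Assignment/Randomization) has tables generated in Excel give each patient a number; an even number means methylprednisolone and an odd number ketorolac. It states: "The statistician will use an equally weighted random number generator to create these assignments". The consequence it draws is "Therefore subjects will have an equal chance of being assigned to either treatment arm". On sex it says: "Separate lists for male and female participants will also be generated to ensure equal gender participation".

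On logistics, "The sealed opaque envelopes will be divided equally among the clinics", and "The research coordinator will open one of the sequentially numbered envelopes to assign each patient the corresponding subject number". Separate envelope sets for men and women are not described, in Section 4.0 or in the dosage and preparation text of Section 6.0. Blocks, an urn, minimisation and quotas by sex appear nowhere in the document.

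Section 9.0 (Statistical Considerations) uses an enrolment ratio of 1, requires 13 completers per arm, and aims at "including a total of 40 patients in the study, which correspond to 20 patients per therapeutic arm". Its only planned adjustment is for baseline ASES score, and only if the arms differ on it. Sex is not in the model.

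**The concern.** Section 4.0 supports a statement about probability: each patient is equally likely to receive either drug. Section 9.0 reads as if it also delivered equal arm sizes. In a trial of 40 the two can differ noticeably.

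The sex lists raise a second question. Their stated purpose is equal participation of men and women, but an allocation list acts only after a person has consented, so it cannot determine how many of each sex enrol. The usual reason for separate lists is to balance arms within sex, and that needs some restriction inside each list. Without one, the extra step yields nothing.

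At stake are comparability of the arms in size and sex mix, and, to a lesser degree, precision.

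**Working it through.** **Inputs.** From Section 9.0: SD 12.3, Δ = 12 used as the margin, one-sided α = 0.05 (z = 1.64), power 80%, 20% loss, 40 enrolled. From Section 4.0: probability 0.5 for each arm. Assumptions added here: draws are independent, each patient is lost independently, and the true difference is zero.

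**The plan's own figure.** 2n = 4(1.64 + 0.84)² × 12.3² / 12² = 25.85, so 26 completers or 13 per arm. Then 26/0.8 = 32.5, so 33. The step from 33 to 40 is a rounding up. The figures reproduce.

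**Arm sizes under simple randomisation of 40.** The number X in one arm is Binomial(40, 0.5).
- P(X = 20) = C(40,20)/2⁴⁰ = 12.5%.
- P(16/24 or more uneven) = 2·P(X ≤ 16) = 26.8%.
- P(15/25 or more uneven) = 15.4%.
- P(more uneven than 18/22) = 2·P(X ≤ 17) = 43.0%; the other 57.0% of sequences lie within 18/22.

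**Sex lists.** If every entry on both lists is an independent draw with probability 0.5, each patient's arm is independent of sex and of every other assignment. The joint distribution is the same as from a single list. For illustration, assume 20 men and 20 women (the documents give no split). The chance of 7/13 or more uneven is 26.3% in a given sex, and 1 − (1 − 0.263)² = 45.7% in at least one. The share of men differs between arms by 20 percentage points or more with probability 26.8%. That falls to 22.6% with 16 men and 24 women, and to 18.7% with 12 and 28.

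**Power.** One-sided 5% t-test, noncentrality 12 / [12.3·√(1/n₁ + 1/n₂)], on n₁ + n₂ − 2 degrees of freedom:

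| Completers | Power |
|---|---|
| 13/13 (planned minimum) | 78.0% |
| 16/16 | 85.3% |
| 12/20 | 83.3% |
| 10/22 | 80.4% |
| 9/23 | 78.2% |
| 8/24 | 75.5% |

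The plan's normal formula gives 80.0% at 13/13; the t-test gives 78.0%.

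Averaging over allocation and loss (40 enrolled, each retained with probability 0.8):

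| | Simple randomisation | 20/20 fixed |
|---|---|---|
| Mean power | 84.1% | 84.9% |
| P(power below the 13/13 level) | 4.7% | 1.8% |

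**What blocks would give.** With block sizes of at most 4 (an illustrative choice) and one sequence per sex, the arms can differ by at most 2 within each sex and by 4 overall. The worst split of 40 is then 18/22.

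**The case against.** The strongest reply is that nothing here threatens the result. Simple randomisation is valid and balanced in expectation, and enrolling 40 where 33 are needed absorbs most of the imbalance. That stands, and three stronger readings should be set aside.

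- A reader might infer that the procedure produces no balance at all. It does not guarantee balance, but more than half of all sequences fall within 18/22.
- A reader might point to the chance that some arm ends with fewer than 13 completers: 25.6% under simple randomisation against 6.3% with 20/20 fixed. Thirteen per arm is the requirement for two equal arms, however. An arm of 12 facing one of 20 has 83.3% power, above the 78.0% at 13/13. The relevant contrast is 4.7% against 1.8%.
- A reader might cite extreme splits. With 32 completers, 9/23 or worse has a 2.0% chance, and 9/23 itself still matches 13/13. A split of 8/24 or worse has a 0.7% chance.

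It is also fair to say that absence of blocking is inferred from silence. A shuffled set of the numbers 1 to 40 read as even or odd would give exactly 20/20, and Section 5.0 mentions a separate Study Drug Management Form covering randomisation, which is not in the document. Against that, an equally weighted generator and an equal chance per subject are the language of independent draws, and no shuffle is described.

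Finally, the plan does not claim that the lists balance arms within sex, and it offers no evidence that sex predicts ASES score. Both are true. But the purpose it does give is one that a list cannot serve.

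**Conclusion.** The point holds as a cheap improvement in design and a correction of wording. It is not a flaw that endangers the conclusion. As written, Section 4.0 describes simple randomisation. "which correspond to 20 patients per therapeutic arm" is therefore an expectation met exactly in 12.5% of sequences, and the sex lists add neither balance of arms within sex nor control over who takes part. The power cost is about one percentage point on average.

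The gain from restriction is mainly an assured balance by arm and sex in a 40-patient trial whose only planned adjustment is conditional and omits sex. The figures rest on independent draws, independent 20% loss, the plan's SD and margin, and a true difference of zero; the within-sex figures also rest on an assumed sex split. If the lists were in fact restricted, the imbalance figures no longer apply, and what remains is an incomplete Section 4.0 and a misstated purpose for the lists.

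**What to change.** 1. Generate each sex list in randomly permuted blocks of varying size (for example 2 and 4), with the sizes known only to the statistician. Section 4.0 now leaves the master list with research coordinators as well, so access to it would have to be limited accordingly.
2. Run one central envelope sequence per sex through the research coordinator instead of dividing envelopes among clinics, so that blocks stay intact. Bring Section 6.0, which places the envelopes in each investigator's clinic, into line.
3. State the purpose of the sex lists as balancing treatment arms within each sex, and drop the aim of equal participation.
4. Include sex, as the stratification factor, in the week-12 model.
5. If the lists are already restricted, state the scheme and how the lists map to envelopes.

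The cost is a few lines in the list-generation program, edits to Sections 4.0, 6.0 and 9.0, and one degree of freedom in the model. The drawback is slight predictability near the end of a block, notably for staff who prepare the syringes and know past assignments. Varying block sizes and central opening of envelopes limit it.

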The sealed envelopes that contain each patient's therapeutic arm assignment will be equally distributed to the study staff prior to the enrollment. They will be kept in locked containers in each investigator's clinic. Only study staff will have access to the envelopes. After patient enrollment and informed consent completion, the study staff will open one of the sequentially numbered envelopes and the patient assigned the corresponding subject number written on the outside of the envelope. The study staff will prepare the appropriate injection (see below) for the assigned treatment arm. The syringe will be covered with opaque tape prior to being given to the surgeon for administration. The injection will take place in a private clinic room in compliance with HIPAA guidelines. The surgeon will administer the injection into the subacromial space using standard bony landmarks from the posterolateral approach. After the injection is given by the research MD, the clinic staff will then dispose of the syringe without disclosing the treatment arm assignment to the patient nor the provider. Patients' subject number will be recorded on their consent form and in their electronic medical record. The statistician will unlock the master list only after patient enrollment and follow-up are complete, or if mandated by any regulatory bodies. Blinding will also be uncovered in case of a patient developing an adverse event while being followed in the trial.

Both drugs will be intra-articularly delivered through a single subacromial injection within 30 to 45 minutes. For the methylprednisolone treatment arm, the injection will consist of 9 mL of lidocaine HCl (1% without epinephrine) and 1 mL of methylprednisolone acetate (80 mg/mL). For the ketorolac treatment arm, the injection will consist of 8 mL of lidocaine HCl (1% without epinephrine) and 2 mL of injectable ketorolac tromethamine (30 mg/mL). The total injection volume in each treatment arm will be 10 mL. These drugs are not suitable for multi-dose use. Following administration of the desired dose, any remaining suspension will be returned to IDS.

Modification of Study Intervention/Investigational Product for a Participant

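### Sections 4.0 and 6.0 contradict each other on where the allocation envelopes are kept, who has access to them and who opens them

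*Combined protocol and SAP*

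**What the plan says.** **Section 4.0 (Treatment Assignment/Randomization).** The statistician seals the envelopes and sends all of them to the research coordinator. They are then "divided equally among the clinics and kept in locked containers in the research coordinator's office". Access is ruled out for one group: "The study staff will not have access to the envelopes". The order of events is also given: "After ensuring that the patient has completed the ASES questionnaire (to establish a baseline prior to the injection), the study staff will contact" one of two named people and pass on the patient's name and MRN. The coordinator then opens an envelope from the numbered sequence, and a member of the clinic staff prepares the syringe. The same section says that the statistician and research coordinators have no contact with patients.

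**Section 6.0 (dosage, preparation and administration text).** The envelopes "will be equally distributed to the study staff prior to the enrollment". On storage: "They will be kept in locked containers in each investigator's clinic". On access: "Only study staff will have access to the envelopes". On opening: "After patient enrollment and informed consent completion, the study staff will open one of the sequentially numbered envelopes". On preparation: "The study staff will prepare the appropriate injection (see below) for the assigned treatment arm".

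**Elsewhere.**
- Section 3.0 requires consent before enrolment. It recruits from the investigators' private clinics and lets a patient who declines the trial receive an injection of a drug agreed with the physician.
- Section 5.0 mentions a Study Drug Management Form that covers randomization among other matters.
- Section 6.0, on subject compliance, requires the ASES questionnaire before the injection.
- Section 9.0 plans for 40 patients.

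**The concern.** Allocation concealment has to hold at the moment when someone decides whether a particular patient enters the trial. The two sections describe different safeguards for that moment, and staff who follow one depart from the other. A monitor could not say which practice complies, and the final report could not describe the concealment method from the protocol.

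The two methods also differ in strength. In Section 4.0 a person without patient contact holds the envelopes and is told who the patient is before one is opened. In Section 6.0 the unopened assignments sit in the recruiting clinics and are opened by the staff who hold them, with no step that first registers the patient with anyone independent. Because a patient can leave the trial route and still be injected with an agreed drug (Section 3.0), staff who knew the next assignment would have a practical way to act on it. What is at stake is the comparability of the arms at entry.

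**Working it through.** No plan figure is at issue and no arithmetic applies. The check is a comparison of the two texts.

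| Element | Section 4.0 | Section 6.0 | Can both be followed? |
|---|---|---|---|
| Location | Research coordinator's office | Each investigator's clinic | No, as written |
| Access | Study staff have none | Study staff only | No |
| Opener | Research coordinator | Study staff | No |
| Steps before opening | Baseline ASES done; name and MRN passed on | Enrolment and consent done | Yes |

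1. **Location.** Office and clinic are different places. Section 4.0 is itself unclear, because the same sentence divides the envelopes among the clinics and keeps them in the coordinator's office. It can be read as sets earmarked by clinic but stored centrally, though it does not say so.

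2. **Access.** The two statements are opposites about the same envelopes. Reading the coordinator as one of the study staff does not help: Section 4.0 has study staff contact a named person, has the coordinator open the envelope, and denies study staff access. It treats them as separate roles.

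3. **Opener.** This differs for the same reason.

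4. **Steps before opening.** Consent, then baseline ASES, then envelope satisfies both wordings, so this is not a contradiction. Section 6.0 is less complete, however. Its custody text names neither the baseline ASES nor the passing of the patient's identity as a condition for opening, and its compliance text places ASES only before the injection. Read alone, it would let the envelope be opened before the self-reported baseline is recorded. Section 9.0 may use that baseline as a regression covariate.

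5. **Precedence.** Neither section is an amendment log, and neither is said to override the other. Section 5.0 gives the Study Drug Management Form no precedence, and the Form is not among the documents.

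6. **Preparer (minor).** One sentence in Section 6.0 has study staff prepare the syringe. Section 4.0 and the accountability text of Section 6.0 say clinic staff. Neither term is defined.

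The count is three contradictions and one gap.

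**The case against.** The strongest reply is that little follows from this in practice. Both sections use sealed, sequentially numbered envelopes in locked containers, and Section 6.0 opens one only after enrolment and consent. Section 4.0 assigns arms by odd or even numbers from a generator with equal weights and states no blocking, so past assignments do not reveal the next one. Neither section names the investigators, who offer the injection and obtain consent, as envelope holders. Study staff is an undefined term, so the people holding envelopes under Section 6.0 need not be those who deal with patients at baseline. The Form may already state the working procedure.

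Most of this stands, and it limits the consequence: selection would still need someone to breach a seal, a lock or the sequence. It does not remove the contradiction. Undefined terms cannot reconcile no access with exclusive access, and an unseen form without stated precedence cannot settle which section governs.

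A reader might go further in four ways that the documents do not support:
- **The trigger for opening is a fourth incompatibility.** It is not, since one sequence meets both sections.
- **Selection bias occurred or is likely.** No breach is described, and actual practice cannot be inferred from the text.
- **Outcome assessment is compromised.** Blinding of patient and surgeon is intended under both sections, and Section 5.0 has a blinded caller collect the follow-up ASES.
- **Keeping the master list with coordinators as well as the statistician defeats concealment.** Section 4.0 says that they have no patient contact and that the statistician alone unlocks the list.

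**Conclusion.** The point holds as an internal inconsistency that should be fixed. Sections 4.0 and 6.0 cannot both be followed on location, access and opener, and Section 6.0 is incomplete on what must precede opening. Its reach is all 40 planned assignments, but that describes scope, not harm: the documents give no means of computing a bias.

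The conclusion that Section 6.0 protects less well rests on two readings: that its study staff work in the clinics where the envelopes are stored, and that the named contacts in Section 4.0 are research coordinators without patient contact. The contradictions on access and opener depend on neither. The statement that selection would need a breach assumes that the list has no blocking or other restriction, as none is stated.

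**What to change.** Replace the custody text in Section 6.0 with the Section 4.0 procedure, in identical words in both sections:

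1. The research coordinator holds all envelopes centrally, and study staff have no access.
2. After consent and a completed baseline ASES, study staff give the coordinator the patient's name and MRN.
3. The coordinator then opens the next envelope in sequence on that patient's sex list and discloses the arm only to the person preparing the syringe. That role is named the same way in both sections.

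In Section 4.0, either say that dividing the envelopes among clinics means sets earmarked by clinic and stored centrally, or delete the phrase. If sets are kept, the sequence in step 3 runs within the set. Check that the Study Drug Management Form says the same.

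The cost is wording in two sections, IRB approval of the amendment (required by Section 10.0), one check of the Form, and the return of any envelopes already placed in clinics. Staffing numbers are not given, but Section 4.0 already provides for the contact at each enrolment, so no new step is added to it.
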